### **Assessing Severity of Adverse Events**

AEs will be graded on a 3-point scale (mild, moderate, severe) and reported in the detail indicated on the eCRF. The definitions are as follows:

Mild	Discomfort noticed, but no disruption of normal daily activity
Moderate	Discomfort sufficient to reduce or affect normal daily activity
Severe	Incapacitating, with inability to work or to perform normal daily activity

The criteria for assessing severity are different than those used for seriousness (see [Section 9.5.1.6.2](#) for the definition of an SAE).

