#### *Classification of Causality*

The relationship of each AE to the study drug will be recorded on the eCRF in response to the following question:

Is there a reasonable possibility that the study drug caused the AE?

Yes (related) A causal relationship between the study drug and the AE is a reasonable possibility.

No (not related) A causal relationship between the study drug and the AE is not a reasonable possibility.

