#### 5.3.5.2 Safety

The algorithm on the assumptions used for imputing the missing dates for AEs is given in the programming specifications.

If the day and month are missing, events will be considered treatment-emergent if the year is equal to or after the year of the first dose date; if days are missing, events will be considered treatment-emergent if the year is after the year of the first dose, or if the year is equal to the year of the first dose date and the month is equal to or after the month of the first dose date.

For the purpose of summarizing maximum severity, if the severity of an adverse event (AE) is missing for a subject, then, if this subject has another AE with the same preferred term that has “severe” severity, the maximum severity of the AE will be noted as “severe”; otherwise the maximum severity will be noted as missing. Similarly, for the purpose of summarizing closest relationship, if the relationship of an AE to study drug is missing, the AE will be noted to be related if there is another related AE with the same preferred term, otherwise this relationship will be noted as missing.

The algorithm to impute missing dates for concomitant medications is given in the programming specifications. No special handling of missing data is planned for the analysis of any other safety variables.

Data exceptions or outliers will be determined by inspection of the tables, listings, and graphs in consultation with the clinical study team. The effect of outliers on analyses may be assessed by re-analyzing the data without the outliers.

All the listings will display the original missing values.

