### 5.6.2 Adverse Events

The AE verbatim descriptions (investigator terms from the eCRF) will be classified into standardized medical terminology using the Medical Dictionary for Regulatory Activities (MedDRA). AEs will be coded to the MedDRA (most recent version) lower level term closest to the verbatim term. The linked MedDRA preferred term (PT) and primary system organ class (SOC) are also captured in the database.

A treatment-emergent AE (TEAE) is defined as an AE that emerged during treatment, having been absent at pretreatment (Baseline) or

- Reemerged during treatment, having been present at pretreatment (Baseline) but stopped before treatment, or
- Worsened in severity during treatment relative to the pretreatment state, when the AE was continuous.

Only those AEs that are treatment emergent will be included in summary tables. All AEs, treatment emergent or otherwise, will be presented in subject data listings.

The TEAEs will be summarized using the Safety Analysis Set. The incidence of TEAEs will be reported as the number (percentage) of subjects with TEAEs by SOC and PT. A subject will be counted only once within an SOC and PT, even if the subject experienced more than 1 TEAE within a specific SOC and PT. The number (percentage) of subjects with TEAEs will also be summarized by maximum severity (mild, moderate, or severe).

The number (percentage) of subjects with TEAEs will also be summarized by relationship to study drug (Yes [related] and No [not related]).

The number (percentage) of subjects with TEAEs leading to death will be summarized by MedDRA SOC, and PT. A patient data listing of all TEAEs leading to death will be provided.

The number (percentage) of subjects with treatment-emergent SAEs will be summarized by MedDRA SOC, and PT. A patient data listing of all SAEs will be provided.

The number (percentage) of subjects with TEAEs leading to discontinuation from study drug will be summarized by MedDRA SOC and PT. A subject data listing of all AEs leading to discontinuation from study drug will be provided.

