### 8.2.3 Handling of Replicate Data

A subject having an AE coded to the same preferred term more than once during the study will be counted only once in the incidence calculations for that AE. Similarly, if a subject has more than one AE in a single body system, the incidence will be counted only once for that body system. If a subject has the same AE more than once, the occurrence that is of greatest severity will be used in the calculation of the incidence of individual AE by severity. Similarly, the AE considered most closely related to study drug will be used in the calculation of incidence of individual AE by relationship.

For the vital signs, EpiTrack, BDI-II, PSQI, QOLIE-31, and C-SSRS datasets, the measurement noted as the scheduled visit measurement will be used in the analysis. If more than one assessment is present at a scheduled visit, then the nearest assessment for evaluation visit(day) will be used in the summaries of the actual values and changes from baseline. In the event of two assessments being equally close to the scheduled visit day, the last assessment will be used.

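### SAP 5.3.5.2 turns a recorded mild, moderate or not-related grade into 'missing' when another event of the same term is ungraded, at odds with SAP 8.2.3

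*SAP*

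**What the plan says.** The protocol grades severity as mild, moderate or severe (Assessing Severity of Adverse Events). It records causality as a Yes/No answer to one question, "Is there a reasonable possibility that the study drug caused the AE" (Classification of Causality).

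SAP 5.3.5.2 covers incomplete grading. Its severity rule is triggered "if the severity of an adverse event (AE) is missing for a subject". If the subject has another event of the same preferred term that is severe, the maximum is severe; "otherwise the maximum severity will be noted as missing". For causality, an unanswered event becomes related if another event of that term is related; "otherwise this relationship will be noted as missing".

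SAP 8.2.3 covers repeated events. A subject counts once per preferred term, and "the occurrence that is of greatest severity will be used in the calculation of the incidence of individual AE by severity". For causality, the most closely related occurrence is used.

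SAP 5.6.2 describes the tables. Subjects with TEAEs are "summarized by maximum severity (mild, moderate, or severe") and "summarized by relationship to study drug (Yes [related] and No [not related"]). Protocol 9.7.1.8.2 gives the same categories. Neither text lists a missing category. The table shells are in a separate document (SAP 11) that is not available here.

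**The concern.** A rule for missing grades should either recover information or report plainly that it is absent. This one does neither when a subject has one graded and one ungraded event of the same term. A subject with one moderate headache and one ungraded headache is known to have had at least a moderate headache, yet the rule reports the maximum as missing. SAP 8.2.3 would report moderate. The SAP does not say which section takes precedence, so two programmers could follow it and produce different tables.

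Safety and tolerability is a secondary endpoint (SAP 5.1.2) and there is no control arm (SAP 5.4), so the absolute counts by severity and relationship are themselves the result. Enrollment also stopped short of the planned size (SAP 7), which gives each subject more weight in every percentage.

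**Working it through.** The plan states no figure on this point, so the check is logical: apply each section to the same records and compare.

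**Inputs.** Three ordered severity grades and two causality answers (protocol); one count per subject and preferred term (SAP 5.6.2); the missing-grade rule (SAP 5.3.5.2); the repeated-event rule (SAP 8.2.3). The reading is the ordinary one: all events belong to one subject, share one preferred term and are treatment-emergent. Under 8.2.3 the highest recorded grade counts, since an ungraded record offers no grade to compare.

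**Step 1. Simple cases.**

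| Records for one term in one subject | SAP 8.2.3 alone | SAP 5.3.5.2 |
|---|---|---|
| severe + ungraded | severe | severe |
| moderate + ungraded | moderate | missing |
| mild + ungraded | mild | missing |
| ungraded only | missing | missing |
| related + unanswered | related | related |
| not related + unanswered | not related | missing |
| unanswered only | missing | missing |

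**Step 2. All patterns of one to four events with at least one ungraded, ignoring order.**

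| | Severity | Causality |
|---|---|---|
| Patterns in total | 35 | 20 |
| Severe (related) cases added by the rule | 0 | 0 |
| Known grade turned to missing | 16 (6 mild, 10 moderate) | 6 (not related) |
| Unchanged, already severe (related) | 15 | 10 |
| Unchanged, nothing graded | 4 | 4 |

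The rows add up: 16 + 15 + 4 = 35 and 6 + 10 + 4 = 20. These are counts of possible patterns and say nothing about how often each occurs.

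**Step 3. Size.** A grade is lost only if the subject has an ungraded event and also a graded, non-severe (or not-related) event of the same term. The documents give no missing rate, so the following is assumption. Let q be the chance that a record is ungraded, and let a subject have one pair of same-term events. The chance that exactly one of the two is ungraded is 2q(1 − q):

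- q = 1%: 2 × 0.01 × 0.99 = 2.0%
- q = 5%: 2 × 0.05 × 0.95 = 9.5%

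If 20% of subjects have such a pair, the share affected is 0.20 × 2.0% = 0.4% to 0.20 × 9.5% = 1.9%. These figures are slightly too high, because the graded event of the pair must also be non-severe (or not related).

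**The case against.** The strongest defence is that the rule is coherent. With one moderate and one ungraded event, the true maximum is moderate or severe, and only a recorded severe settles it. Calling the maximum missing avoids claiming that the event was at most moderate. This is a fair description of the uncertainty, but it does not justify reporting a subject known to have had at least a moderate event as if nothing were known.

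It can also be argued that there is no true conflict. SAP 8.2.3 is a general rule that does not mention missing grades, and 5.3.5.2 is the specific one and so governs. That is a possible reading, but the SAP does not state it, and the two sections applied as written still give different answers.

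Three further points stand and limit the finding:

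- A reader might infer that affected subjects drop out of the tables. That cannot be established: the shells may contain a missing row, and 5.3.5.2 itself tells the programmer to note the value as missing.
- The statement that the rule adds no severe or related case depends on the ordinary reading. SAP 5.3.5.2 speaks of another AE, not another TEAE, and AEs are recorded from consent (protocol 9.5.1.6.1). If a severe event that is not treatment-emergent could trigger the rule, it would add a severe case in 20 of the 35 patterns (6 + 10 + 4, those without a severe TEAE). The causality sentence also does not repeat that the other event must be in the same subject, although its link to the severity sentence points that way.
- Grading may be nearly complete. Investigators are asked to make every effort to classify each event (protocol 9.5.1.6.1), and the eCRF is signed for completeness (protocol 9.6.1).

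**Conclusion.** The point holds as a defect in a derivation rule with limited reach. On the same-subject, TEAE-only reading, the rule's only effect is to replace recorded mild, moderate or not-related grades with missing, which conflicts with SAP 8.2.3 and produces a category that the text of SAP 5.6.2 and protocol 9.7.1.8.2 does not list.

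Two stronger readings are not supported. First, a reader might infer that the rule understates severe or drug-related events. It does not: relative to 8.2.3 those counts are unchanged, as are overall TEAE incidence and the listings, which keep the original missing values. An event that is the only one of its term and has no grade is missing with or without the rule. Second, a reader might take the share of subjects with any ungraded record, 1 − (1 − q)^r, as the size of the problem. For q = 1% and r = 3 records it is 3.0%; for q = 5% and r = 5 it is 22.6%. That omits the need for a graded event of the same term in the same subject. The 0.4% to 1.9% above is nearer the mark, but it rests on an assumed missing rate and an assumed 20% of subjects with a same-term pair. The effect is probably small, and close to zero if the eCRF enforces grading.

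The case for correction rests on the inconsistency, which exists whatever the missing rate.

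**What to change.** In SAP 5.3.5.2, replace the severity rule with a statement that maximum severity is the highest recorded severity among that subject's TEAEs of the preferred term, as in 8.2.3, and that an ungraded record does not override a recorded grade. Naming the subject and TEAEs also removes the looser readings. For causality, state one convention consistent with 8.2.3, such as using the most closely related recorded answer. Where no occurrence is graded or answered, show a missing row with its count, and add that category to SAP 5.6.2.

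A worst-case summary that counts wholly ungraded events as severe or related could be added as a footnoted sensitivity analysis, but it is not required. It should not be the main rule: it would put unobserved grades into the counts of an uncontrolled study. If every unanswered event were counted as related, a missing answer would also override a recorded not-related one.

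The cost is a few sentences of SAP text and a few lines of code. No additional data are needed.

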### 5.3.6 Other Considerations

Not applicable.

## 5.4 Efficacy Analyses

This is a study without a control arm. Therefore, only descriptive statistics will be performed. The SAS will be used to summarize retention rate and the FAS will be used to summarize

seizure data.

#### 5.4.1 Primary Efficacy Analyses

The retention rate, defined as the proportion of subjects remaining on perampanel treatment at 3, 6, 9, and 12 months after initiation of treatment, will be summarized. The number and percentage of subjects remaining on treatment at each time point will be summarized using SAS. Corresponding 95% CIs may also be presented if allowed by the data.

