#### Maintenance Period

Subjects will continue to receive the perampanel dose level that was administered at the end of the Titration Period, when they enter the 39-week Maintenance Period. Subjects will come to the study site for Visit 4 (Week 13), Visit 5 (Week 26), Visit 6 (Week 39), Visit 7 (Week 52), and at the Follow-Up Visit (Visit 8). All subjects who discontinue the study are to complete the study's early discontinuation procedures indicated in the Schedule of Procedures/Assessments. (revised per Amendment 01)

According to the investigator's clinical judgment, subjects who experience AEs may have their perampanel dose reduced. Conversely, if seizures are not adequately controlled, subjects may have their dose increased up to a maximum of perampanel 12 mg. During the Maintenance Period, subjects whose perampanel dose has been reduced may have the dose increased again, at the discretion of the investigator, as soon as tolerability improves. Subjects who cannot tolerate a dose of 4 mg will discontinue perampanel treatment and be withdrawn from the study. Adjustment of the concomitant AED dose level during the Maintenance Period is permitted. Subjects who receive perampanel as a 1st adjunctive therapy may also be converted to perampanel monotherapy at the discretion of the investigator. All adjustments to concomitant AED dose levels must be reported in the eCRF.

The overall study design is depicted in [Figure 1](#).

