#### 9.3.3.2 Withdrawals

Subjects who were administered at least 1 dose of study drug but could not participate in the study are classified as 'withdrawals'. The investigator may withdraw the subject from the study at any time for safety or administrative reasons. The subject may stop study drug or withdraw from the study at any time for any reason.

Reasons for withdrawal are as the following:

- Withdrawal of informed consent
- AE(s) requiring discontinuation of study therapy
- Eligibility violation
- Lack of efficacy
- Administration of prohibited medications
- Lost to follow-up
- Unable to continue the study in the investigator's judgment

The investigator will make every reasonable effort to follow up subjects for any AEs. He/she will use all possible ways to communicate (phone call, letters, and visit to home) with the subject. The reason for withdrawal should be documented on the eCRF. Final assessments of withdrawn subjects should be conducted and documented as described in [Section 9.6.1](#). Withdrawn subjects will not be allowed to re-enter the study.

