#### 9.4.7 Prior and Concomitant Drug/Therapy

- Concomitant AED for subjects who receive perampanel as a 1st adjunctive therapy

- Only 1 AED can be used.
- A concomitant AED must be used at the stable dose and administered between 8 weeks before Visit 2 (Week 0) and the end of the Titration Period. The dose and administration of the AED may be modified during the Maintenance Period based on the investigator's judgment.
- Concomitant medication  
The following concomitant drugs are prohibited throughout the study period (up to the Follow-Up Period or early discontinuation visit): (revised per Amendment 01)
  - CYP3A4-inducing drugs and food below as follows (from 30 days before Visit 1): Rifampicin, troglitazone, barbiturates except for use as AED, modafinil, efavirenz, nevirapine, glucocorticoid except for topical use, pioglitazone, rifabutin, and food containing St. John's Wort (*Hypericum perforatum*). (revised per Amendment 01)
  - Antipsychotics
  - Other investigational drugs. (revised per Amendment 01).
  - CBD products (revised per Amendment 01)Restricted concomitant drug:
  - Any changes in the dosing regimen of antidepressant or antianxiety drugs during the study must be recorded.
  - Barbiturates (except for seizure control indication and premedication for EEG) and benzodiazepines (except for seizure control indication) within 8 weeks prior to Visit 2 (Week 0)
- Concomitant therapy (revised per Amendment 01)  
Prohibited concomitant therapy  
The following therapies must not be implemented during the study:
  - Investigational deviceRestricted concomitant therapy:
  - Vagus nerve stimulation is allowed, but stimulator parameters cannot be changed for 8 weeks before Visit 2 (Week 0) or thereafter during the study.
  - A ketogenic diet will be allowed as long as the subject has been on this diet for 8 weeks prior to Visit 2 (Week 0). Additionally, a ketogenic diet cannot be newly added or discontinued during the study.Clarification of previous AED medication:
  - Subjects may switch monotherapies provided the time to complete the conversion is less than 30 days.
  - Subjects on short-term monotherapy (<2 weeks) may be eligible for the study provided they stop the initial therapy at the time of perampanel dosing.

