#### **9.5.1.2      Efficacy Assessments**

Exposure data will be utilized to assess the primary endpoint. Secondary efficacy variables will be based on seizure frequency. Seizure frequency data will be collected in subject diaries by subjects or guardian/legally authorized representative during the study including the Titration Period and the Maintenance Period. Baseline seizure frequency data for up to 12 weeks before Visit 2 (Week 0) will be collected by subjects or guardian/legally authorized representative, retrospectively (for history prior to screening) and prospectively (during baseline). Subjects will be eligible for study enrollment after they have experienced the 2 unprovoked (or reflex) seizures occurring greater than 24 hours apart, or 1 unprovoked (or

reflex) seizure with EEG evidence of seizures, and will not need to complete the full 12-week diary to enter the Titration Period. (revised per Amendment 01) Seizure frequency data in subject diaries will be reviewed with the investigator(s) at Visit 2, 4, 5, 6, and 7. Seizure frequency from diary entries or principal investigator verification will be used to assess efficacy endpoints as appropriate. (revised per Amendment 01)

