### 9.7.1.1 Study Endpoints

#### 9.7.1.1.1 PRIMARY ENDPOINT

The primary endpoint is retention rate, defined as the proportion of subjects remaining on perampanel at the specified time points: 3, 6, 9, and 12 months after initiation of treatment.

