#### 3.1 Study Objectives

##### 3.1.1 Primary Objective

To assess the retention rate of perampanel when given as monotherapy or 1st adjunctive therapy in subjects with partial-onset seizures (POS) or primary generalized tonic-clonic seizures (PGTCS).

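### Retention is planned only as still on perampanel, with no summary by starting setting and none of monotherapy starters who remain on perampanel alone

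*SAP*

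**What the plan says.** **Objective.** SAP 3.1.1 reads "To assess the retention rate of perampanel when given as monotherapy or 1st adjunctive therapy", so it names two treatment settings. Protocol 8.1 says the same.

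**Endpoint.** Protocol 9.7.1.1.1 states: "The primary endpoint is retention rate, defined as the proportion of subjects remaining on perampanel at the specified time points", at 3, 6, 9 and 12 months. SAP 5.1.1 repeats this, and SAP 5.4.1 analyses retention "defined as the proportion of subjects remaining on perampanel treatment at 3, 6, 9, and 12 months after initiation of treatment". None of these places sets a condition on other AEDs. Protocol 9.5.1.2 gives the data source: "Exposure data will be utilized to assess the primary endpoint".

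**Breakdowns.** SAP 5 and 5.3.4 summarise retention by seizure type and overall, and 5.3.4 adds sex and age group. Starting setting is not listed.

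**AED status as an outcome.** SAP 5.1.2 and 5.4.2 count subjects who go from 1st adjunctive therapy to perampanel monotherapy. Nothing counts monotherapy starters who add an AED.

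**Rules on AEDs.** Protocol 9.4.7 says "Only 1 AED can be used", under the heading for 1st adjunctive subjects; Protocol 9.2.3 justifies the limit for that setting only. The prohibited list in 9.4.7 does not name the addition of an AED. Protocol 9.3.3.2 lists "Administration of prohibited medications" among the withdrawal reasons, with lack of efficacy and investigator judgment. For 1st adjunctive subjects the background AED dose is fixed through Titration; after that, Protocol 9.1.3 says: "Adjustment of the concomitant AED dose level during the Maintenance Period is permitted".

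**Data.** Protocol 9.5.1.1.5 collects AED treatment throughout the study, and 9.1.3 requires concomitant AED dose changes to be entered in the eCRF.

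**The concern.** Protocol 7.2 justifies the study partly by the scarcity of clinical-study information on perampanel as monotherapy. A single pooled figure for subjects still on perampanel does not answer that. It mixes two starting settings that the objective names separately. Within the monotherapy setting, it does not separate subjects held on perampanel alone from any who needed a second AED.

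The plan is also one-sided. It treats the move from two drugs to one as an outcome, but has no counterpart for the move from one drug to two.

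Seizure freedom has a related gap. All three seizure-free windows lie in Maintenance, which is when the background AED dose may be changed. SAP 5.4.2 counts early dropout as not seizure-free but has no rule for a background dose increase or an added AED before the window ends.

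**Working it through.** **No planned figure to reproduce.** The sample of about 125 comes with no hypothesis, assumed retention rate, precision target, alpha or power (SAP 4). The point rests on the definitions; the arithmetic shows scale only.

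**Step 1: what the planned tables can answer.**

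| Question raised by the objective | Planned summary |
|---|---|
| How many stay on perampanel overall? | Yes, SAP 5.4.1 |
| By seizure type, sex, age group? | Yes, SAP 5.3.4 |
| Among monotherapy starters and 1st adjunctive starters separately? | None |
| How many monotherapy starters are on perampanel alone? | None |
| How many 1st adjunctive starters reach monotherapy? | Yes, SAP 5.4.2 |

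**Step 2: whether the missing rows can be derived.** The Schedule of Procedures/Assessments records concomitant AED at Weeks 13, 26, 39 and 52 (Days 92, 183, 274 and 365), which match the 3, 6, 9 and 12 month time points. The telephone contact at Week 4 has no such entry, but it is not a retention time point. No new data collection is needed.

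**Step 3: switchers.** Protocol 9.4.7 allows a change of monotherapy if conversion takes under 30 days. If those days run from the first perampanel dose (an assumption; the protocol does not give the starting point), the overlap ends well before Day 92. A rule is still needed so that a tapered prior AED is not read as an added one.

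**Step 4: illustrative size.** The documents give neither input, so both are assumptions. R is the share of monotherapy starters on perampanel at 12 months; a is the share of those taking an added AED.

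- Retention on perampanel alone = R × (1 − a)
- Gap from the planned rate = R × a

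With R = 70%:

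| a | On perampanel alone | Gap (points) |
|---|---|---|
| 5% | 70 × 0.95 = 66.5% | 3.5 |
| 10% | 70 × 0.90 = 63.0% | 7.0 |
| 20% | 70 × 0.80 = 56.0% | 14.0 |
| 30% | 70 × 0.70 = 49.0% | 21.0 |

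For R from 50% to 80% and a from 5% to 30%, the gap runs from 50 × 0.05 = 2.5 points to 80 × 0.30 = 24.0 points.

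**Step 5: precision, for scale.** If all 125 planned subjects had been enrolled and 88 retained (70.4%), the 95% Clopper-Pearson interval would be 61.6% to 78.2%, a half-width of (78.2 − 61.6)/2 = 8.3 points. SAP 7 says enrolment stopped short of plan, and monotherapy starters are only part of the sample, so a rate by setting will be less precise than this.

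**The case against.** The strongest reply is that the endpoint is a stated choice. Protocol 9.2.2 explains that retention is used in studies resembling practice because it reflects efficacy and safety together. Staying on perampanel whatever else is adjusted is a coherent measure. This stands: the definition is not an error and should not be replaced.

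A reader might go further in four ways that the documents do not support.

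- **That retention on monotherapy cannot be measured.** The AED data are collected; what is missing is a definition and a planned summary. The table shells are in a separate document (SAP 11) that was not available.
- **That sites will give the same clinical course opposite primary outcomes, one keeping the subject and another withdrawing.** The concomitant-AED passages leave this open, but nothing shows that it happens. The protocol can also be read as allowing no AED in monotherapy subjects: the one-drug allowance is written for adjunctive use, adding an AED is not among the changes described for Maintenance, and lack of efficacy is a withdrawal reason. The silence is real; divergent classification is conjecture.
- **That background AEDs may be raised without limit.** Changes are barred in Titration, follow the investigator's judgment in Maintenance and must be recorded.
- **That the plan credits such seizure freedom to perampanel.** SAP 5.4 is descriptive with no control arm, so it makes no causal claim. The narrower fact is that the seizure-freedom rule does not separate these subjects.

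It is also fair to say that early termination of enrolment will leave small counts, and that a protocol clarification comes late. Neither prevents the derived SAP summaries.

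**Conclusion.** The point holds as a gap in the planned summaries, not as a fault in the primary endpoint. The objective names two starting settings and the rationale stresses monotherapy, yet the SAP reports retention neither by setting nor on perampanel alone. The related omission in SAP 5.4.2 also holds.

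The documents give no retention rate, no rate of AED addition and no split between settings, so the size of any gap is unknown. The 49% to 66.5% range, against 70%, rests wholly on the assumed inputs and predicts nothing about this trial. If no monotherapy starter added an AED, the gap would be zero, and the added row would show that. This is an inexpensive improvement worth making.

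**What to change.** **SAP 5.4.1.** Keep retention as defined as the primary summary and add:

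- (a) retention at 3, 6, 9 and 12 months by starting setting (monotherapy or 1st adjunctive), with starting setting defined;
- (b) for monotherapy starters, the proportion on perampanel with no other AED at each time point, with all monotherapy starters in the Safety Analysis Set as denominator. State that a prior AED withdrawn within the under-30-day conversion is not an added AED.

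**SAP 5.4.2.** Add a supportive summary of seizure freedom with no AED added and no background AED dose increase before the end of each window.

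**Protocol 9.2.3, 9.3.3.2 and 9.4.7.** These do not say how an AED added in a monotherapy subject is treated. The sponsor should reconcile them; the clinical rule is the sponsor's to set. With enrolment closed, this mainly puts the rule on record.

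**Cost.** Derivation and table programming over four time points and three seizure-free windows, but no new data. The added rates cannot exceed the matching headline rates, except that retention by setting may fall either side of the pooled rate. The counts will be small and imprecise and should be reported as counts with denominators.
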